#### **SPECIFIC AIMS**

We will accomplish these goals with three specific aims. First, we will integrate the KIU! intervention into a widely-used health technology platform to increase its scalability, adaptability, and potential for broad implementation. Second, we will test the efficacy of the KIU! eHealth intervention in a multisite RCT by: a) enrolling ethnically diverse YMSM (N = 900; > 65% racial/ethnic minorities) who tested HIV negative in the clinics of our community partners in Chicago, New York, and Atlanta. We anticipate that approximately 4500 YMSM will have to be screened to enroll this number of YMSM; b) randomizing participants to either the KIU! intervention or an HIV knowledge control condition; and c) measuring intervention outcomes at baseline and follow-up assessments at 3, 6, and 12 months. The primary behavioral outcome will be the count of unprotected anal sex acts and the primary biomedical outcome will be STI incidence. And third, we will explore if the KIU! intervention has differential efficacy across important sub-groups of YMSM based on race/ethnicity, relationship status (serious versus casual relationships), and gay/bisexual identity.

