Similar procedures and measures successfully used in the developmental study will be employed. Assessments will be completed via the Internet using a Computer-Assisted Self Interview (CASI). We will administer knowledge/information based measures immediately post-intervention along with the measures of intervention acceptability and tolerability. Motivation, skills (i.e. partner sexual communication, correct condom use), and behavioral outcomes (i.e. number of insertive and receptive unprotected anal sex acts, condom errors) will be measured at all follow-up points. Whenever possible, we selected measures: (1) designed for high-risk YMSM to maximize sensitivity, (2) previously tested with diverse populations to minimize cultural bias, and (3) to maximize comparability to other studies in order to compare findings. All measures and a table depicting what is assessed at each time-point can be found in Appendix 2. Participants will be paid for completing assessment waves (~30 minute duration; See Budget Justification). As we have done successfully in prior online studies, participants will be given the option of receiving payment in person or via mail.

|                     | Construct                                       | Measure   |
|---------------------|---|---|
|                     | Administration Points                           |   |
| Primary
Outcomes | Unprotected sex acts and HIV testing  BL 3 6 12 | The AIDS-Risk Behavior Assessment (ARBA)  has been used with YMSM  and assesses behaviors on a partner-by-partner level, starting with recent partners, as well as in the aggregate. Partners are classified as serious or casual and relationship duration is measured  . Questions differentiate between insertive and receptive anal sex. The ARBA will also assess secondary outcomes of HIV testing behaviors. |
| P Q                 | STI incidence                                   | CT and GC testing of urine and rectal samples using the FDA cleared Gen-Probe APTIMA  |

|                    | BL 3 6 12   | Combo 2 Assay. All participants will be tested at baseline and 12 month follow-up. Participants who test positive at baseline will also be tested at 3 month and 6 month follow-ups.  |
|--------------------|---|---|

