(h) STI biomarkers: Our approach to the distance STI testing follows [name]'s effective protocol for the Checking In Study (see C.2.d). To test for STIs, we utilize at-home urine collection kits and at-home rectal swab test kits which both use the FDA approved Gen-Probe APTIMA Combo 2® Assay, a target amplification nucleic acid probe test that utilizes target capture for the in vitro qualitative detection and differentiation of ribosomal RNA from CT and NG. Gen-Probe reports sensitivity of 98 – 100% and specificity of

98%- 100% for urethral CT and NG. Urine and rectal samples will be tested in the Centers for Disease Control and Prevention (CDC) Division of STD Prevention Laboratory.

STI testing protocol at baseline will vary based on enrollment site. Participants who enroll off-site (e.g. at home or at a library) will be shipped both test kits in a nondescript box. Easy-to-understand instructions for collecting and returning the samples will be provided with the kits. In addition to the written instructions provided with the rectal STI kit, a private video with instructions for properly collecting the rectal samples will be shared with participants. The sample collection kits are identified by study ID only. After the samples are returned through the mail and processed by the CDC lab, results will be sent on at least a biweekly basis to Northwestern University. If a specimen is not received within 3 weeks of mailing, an electronic reminder will be sent through the medium chosen by the participant (text message or email) or phone if no preferred medium was selected by the participant. Repeat reminders will be sent in subsequent weeks if the specimen remains unreturned and, eventually, telephone follow-up will be used to support participants whose specimens were overdue by 4 weeks from time of mailing. The STI testing protocol at all follow-ups will be the same for these participants.

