**B.11. RCT Analytic Plan.** This is a two-group, active-control, RCT of an online intervention. The study's hypothesis concerns between-group differences in the change in HIV/STI risk behavior and STI incidence from pre-intervention to later follow-ups. There are 4 assessment points of RCT outcomes: baseline, 3, 6, and 12 months post-intervention. Prior to conducting full analyses, standard descriptive analyses will be conducted to check for invalid values, outliers, and logical consistency between variables. We will assess the comparability of the experimental and control groups at baseline. If any variables differ significantly at baseline, they will be included as covariates in the adjusted outcome analyses along with variables known from prior research (e.g. age) to be correlated with the outcome under analysis. Following extensive data description and analysis at separate follow-up points, the primary analysis will utilize all follow-up points by fitting mixed effect regression models. Also known as hierarchical linear models (HLM) , these models allow for the presence of missing data, time-varying or invariant covariates, and subject measurement at different time points. HLM models appropriate to the characteristics of the distribution (i.e. normal, Poisson) will be fit using SAS.

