The primary behavioral outcome measure of treatment success will be the count of unprotected anal sex acts and the biomedical endpoint will be NG/CT incidence (Aim 2). Secondary outcomes include: condom errors, IMB factors, and receipt of an HIV test. We will also explore intervention effects separately for receptive and insertive anal sex. The primary independent variable of interest is the indicator for the intervention group. The baseline value of the outcome and other required covariates at baseline will be included as additional independent variables. The intervention will recruit participants from multiple sites (multiple clinics in three cities); however it is not delivered in groups so site will be adjusted for as a fixed rather than a random independent variable. A random intercept term will be included to account for individual average levels of the outcome. The effect of time will first be estimated as a categorical variable in order to describe and adjust for time trends as observed. A second strategy will start with estimating a single slope reflecting average change across all 4 time points, then add a guadratic term if it contributes significantly to the model. Random effects for time variables, reflecting individual variations in time trends, will be included in addition to random intercepts, if significant. A single effect of group will test the intervention effect averaged across all time points, adjusting for all included covariates and underlying time trends. Potential moderators (race/ethnicity, relationships status, and gay/bisexual identity) will be added as independent variables and their interactions with intervention group will be tested (Aim 3). Addition of interaction terms between time and intervention group will provide a test for comparing time trends in change scores between groups.

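### NG/CT incidence, the primary biomedical endpoint, has no suitable named model: only normal and Poisson random-intercept mixed models are listed, while most men supply one yes/no follow-up result

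*Protocol*

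**What the plan says.** Protocol Specific Aims state that "the primary biomedical outcome will be STI incidence". The assay in B.10(h) is qualitative, designed for "target capture for the in vitro qualitative detection and differentiation of ribosomal RNA from CT and NG", and B.12 states STI power in percentages of men (control incidence 10% to 15%).

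The testing schedule is in the measures table of B.10(d): "All participants will be tested at baseline and 12 month follow-up". It adds: "Participants who test positive at baseline will also be tested at 3 month and 6 month follow-ups".

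The modelling text is in B.11 and is repeated in SAP C3. The distributional statement is "HLM models appropriate to the characteristics of the distribution (i.e. normal, Poisson) will be fit using SAS". Then: "A random intercept term will be included to account for individual average levels of the outcome". Baseline is a covariate: "The baseline value of the outcome and other required covariates at baseline will be included as additional independent variables". A single group term tests the intervention effect averaged over the time points. None of this is varied for the STI endpoint. Neither document names a binomial, logistic or log-binomial model, and neither says how the two anatomical sites, the two organisms, repeat positives and self-reported interim infections combine into NG/CT incidence.

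**The concern.** The modelling text suits the count of anal sex acts, which every man reports at months 3, 6 and 12. NG/CT differs in three ways.

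- **Distribution.** A positive/negative result has variance p(1−p). A Poisson model assumes p, so its model-based standard error is too large.
- **Random intercept.** A man negative at baseline supplies one outcome row. One row carries no information for separating between-man variation from residual variation.
- **Time-averaging.** Month 3 and 6 results exist only for men positive at baseline, so an average over time points gives that selected subgroup extra rows.

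At stake is some power on a primary endpoint, and an analysis choice left open. Protocol B.10(f) already refers to a preliminary look at repeat rectal infections, which is a further reason to fix the model in writing.

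**Working it through.** **Inputs.** 900 enrolled, 80% retained (B.12): 720 men, 360 per arm. Control incidence 10% to 15% (B.12). Baseline prevalence 10.2%, from urine only in an earlier cohort (B.2(c)); 20% and 30% are assumptions to allow for rectal testing. Alpha 0.05, taken as two-sided because the documents do not say.

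**The plan's own power.** B.12 gives 81%, 70% and 56% for reductions of 7, 6 and 5 points from 10%, and 71%, 60% and 47% from 15%. These do not reproduce. A pooled two-proportion test with 360 per arm gives 96.9%, 88.6% and 72.2%, and 83.9%, 69.8% and 52.7%. The sizes implied by the six stated figures run from 199 to 311 per arm, so no single size fits. That is a separate matter; the stated powers are not used below.

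**Follow-up tests per man**, assuming equal retention and complete testing:

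| Baseline prevalence | Men with one test | Men with three tests | Share of rows from baseline-positives |
|---|---|---|---|
| 10.2% | 720 × 0.898 = 647 (90%) | 73 | 220/867 = 25% |
| 20% (assumed) | 576 (80%) | 144 | 432/1008 = 43% |
| 30% (assumed) | 504 (70%) | 216 | 648/1152 = 56% |

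**Poisson standard error.** The ratio of Poisson to Bernoulli standard error is √[p/(p(1−p))] = 1/√(1−p). With equal risks in both arms, the actual type I error is 2[1 − Φ(1.96/√(1−p))].

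| Risk p | SE ratio | Type I error |
|---|---|---|
| 10% | 1.054 | 3.9% |
| 15% | 1.085 | 3.4% |
| 25% (assumed) | 1.155 | 2.4% |
| 30% (assumed) | 1.195 | 1.9% |

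**Power on the log risk-ratio scale, 360 per arm.** Let SE_B = √[(1−p₁)/(360p₁) + (1−p₀)/(360p₀)] and SE_P = √[1/(360p₁) + 1/(360p₀)]. The estimate varies with SE_B, but the Poisson test uses SE_P, so its power is Φ((ln(p₀/p₁) − 1.96·SE_P)/SE_B).

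| Comparison | SE_B | SE_P | Power, correct SE | Power, Poisson SE |
|---|---|---|---|---|
| 10% vs 5% | 0.2789 | 0.2887 | 70.0% | 67.6% |
| 15% vs 10% | 0.2018 | 0.2152 | 51.9% | 46.8% |
| 10% vs 3% | 0.3388 | 0.3469 | 94.4% | 93.9% |
| 15% vs 8% | 0.2184 | 0.2307 | 82.1% | 79.0% |

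**Normal model.** In simulations of a linear model on the 0/1 result, one row per man and 360 per arm, type I error was about 5% at risks of 10%, 15%, 25% and 30%.

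**Random intercept.** A small maximum-likelihood simulation (720 men, 25 replicates per scenario, indicative only) gave:

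- One binary result per man, logistic: the 10–90% range of the estimated intercept SD was 0 to 2.48 when the truth was 0, and 0.02 to 2.46 when the truth was 1. The likelihood is flat.
- Three tests in baseline-positives at 10.2% prevalence, logistic: median 0.92 for a true SD of 1, 10–90% range 0.37 to 1.37. This is weakly identified.
- Poisson: the estimate went to essentially zero throughout, because yes/no data vary less than Poisson data.

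**The case against.** The governing clause promises models that suit the distribution, and the parenthesis does not assign Poisson to NG/CT. A careful analyst could fit a logistic model and stay within the text. This stands: a binary model is not excluded, only not named.

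A reader might infer that the STI standard errors will be wrong. The documents do not support that. The error needs the Poisson option together with model-based standard errors; the normal option gives nearly correct standard errors for a risk difference. The error is also conservative, so it does not raise the chance of a false efficacy claim.

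A reader might also infer that the random intercept cannot be estimated at all. Its variance is one parameter for the whole model, and men positive at baseline have three tests, so it is weakly identified. The alternative time strategy, which begins with "A second strategy will start with estimating a single slope reflecting average change across all 4 time points", would give every man tested at both points at least two rows if baseline entered as an outcome, although that conflicts with using baseline as a covariate.

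A larger effect is tempting because the Atlanta rates in B.6 sum to 17.1 (White: 4.5 + 6.7 + 1.5 + 4.4) and 58.0 (Black: 10.5 + 22.9 + 4.4 + 20.2) per 100 person-years. These sums count infections, not infected men, and are not the chance of a positive result on one month-12 test. No Latino rate is given. Risks of 25–30% therefore remain an assumption.

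Finally, NG/CT incidence is never defined as yes/no. Were it a count of infections, Poisson would be natural. The qualitative assay and the percentage-based power statement point the other way, but the gap in definition is real and belongs in the fix.

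**Conclusion.** The point holds as a modest defect in the stated method. The only named models do not fit a single yes/no result per man, and the time-averaged effect does not suit a schedule in which months 3 and 6 are tested only in baseline-positives.

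The size is conditional. With Poisson and model-based standard errors, they are 5% too large at 10% risk and 8% at 15%, type I error is about 3.9% and 3.4%, and the power loss is roughly 2 to 5 points for a five-point reduction (about half a point for 10% versus 3%). At an assumed risk of 25–30% the standard error is 15–20% too large. With a normal model the loss is negligible. The intercept variance is not identified from men with one test, is weakly identified from a selected subgroup, and goes to about zero under Poisson.

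These results assume a yes/no endpoint, 360 men per arm and a two-sided 5% test. The trial's validity is not threatened, but the remedy is almost free.

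**What to change.** In Protocol B.11 and SAP C3:

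1. Define the primary STI endpoint as any positive result, urethral or rectal, NG or CT, at month 12, with one row per man.
2. Analyse it without a random intercept by logistic or log-binomial regression, or by Poisson regression with robust variance; name one. Include arm, baseline NG/CT status, race, site and the plan's other prespecified covariates. Report the adjusted risk difference and risk ratio with 95% confidence intervals.
3. Use the month 3 and 6 tests and the self-reported interim infections in a sensitivity analysis.
4. For receipt of an HIV test, also yes/no, name a logit mixed model. The random intercept can stay there because that outcome is measured at months 3, 6 and 12.

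The cost is a few sentences and no new data. The downside is that the month 3 and 6 tests in baseline-positives leave the primary STI analysis, so the text should say that this is a deliberate exception to using all available measurements.

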#### STUDY DESIGN

This is a two-group, active-control, RCT of the KIU! an online intervention. Participants will be randomized to two groups in equal proportions (KIU! condition n=450; control arm n=450). The KIU! intervention involves 7 modules completed across three sessions, done at least 24 hours apart (i.e., at least 3 days), and totaling ~2 hours to content. Across these modules, the KIU! intervention uses diverse delivery methods (e.g., videos, animation, games) to address HIV knowledge, motivate safer behaviors, teach behavioral skills, and instill self-efficacy for preventive behaviors. The control condition contains the same number of modules as the KIU! condition, with the same requirement to participate across three sessions. It reflects HIV information that is currently available on many websites so as to understand how the KIU! intervention improves upon what is currently available online. Booster sessions will be delivered at 3 and 6 months for each arm.

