B.12. Power and Sample Size. All power calculations were performed in R version 2.14.0 and using common sample size formula for repeated measures with nominal Type I error rates (i.e.  $\alpha$ =.05) and effect estimates based on our preliminary studies. We will screen approximately 4500 YMSM, enroll 900 YMSM, and assume 80% retention based on our preliminary studies. Assuming participants are randomized to two groups in equal proportions, we will have 97% power to detect a 11% reduction in the rate of unprotected sex (ERR = 0.89) due to the intervention, assuming the correlation between repeated measures is 0.8. The correlation among repeated measures plays an important role in the calculation; in this case, our power calculation is conservative if the correlation among repeated measures is, in fact, weaker than 0.8. The smallest effect size with which we will have 80% power to detect is a 6.5% reduction in the rate of unprotected sex. Technically speaking, our study will have greater power than what is reported here after we adjust for our blocked design. In conclusion, we will have 80% power to detect an effect size equal to half of what we observed in our pilot trial and less than half of the lower bound of effect sizes seen in other HIV prevention programs with MSM. For our primary biomedical endpoint of STI incidence, we assume the annual incidence based on our longitudinal cohort studies in the range of 10 to 15%. If the incidence rate in the control group is 10%, we will have 81%, 70%, and 56% power to detect an incidence reduction of 7%, 6%, and 5%, respectively. If the incidence rate in the control group is higher, say 15%, then the power reduces to 71%, 60%, and 47%, respectively. The objective of aim 3 is to estimate the intervention effect among subgroups and test for significant differences. In data analyses, this will be achieved by testing 2-way interactions, treatment by subgroup. For a conservative power calculation, we repeated the power calculations as per aim 1 with a reduced sample size. Assuming N=200 per group (say, for racial/ethnic subgroups), an ERR=0.89 as above, and strong correlation among repeated measures (i.e. 0.8), we will have 91%, 85%, and 77% power to detect a 10%, 9%, and 8% reduction in the rate of unprotected sex among YMSM, respectively, due to KIU! intervention. The power will be less for effect sizes more subtle than 8% and less for smaller subgroups. In addition to racial/ethnic subgroups, other subgroups of interest include sexual orientation identity groups (81% gay, 17% bisexual identified) and relationship groupings (30% recent serious relationships). The power for each subgroup comparison will be similar to the power described above.

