All power calculations were performed in R version 2.14.0 and using common sample size formula for repeated measures²¹⁰ with nominal Type I error rates (i.e. α =.05) and effect estimates based on our preliminary studies. We will screen approximately 4500 YMSM, enroll 900 YMSM, and assume 80% retention based on our preliminary studies. Assuming participants are randomized to two groups in equal proportions (KIU! condition n=375; control arm n=375), we will have 97% power to detect a 11% reduction in the rate of unprotected sex (ERR = 0.89) due to the intervention, assuming the correlation between repeated measures is 0.8. The correlation among repeated measures plays an important role in the calculation; in this case, our power calculation is conservative if the correlation among repeated measures is, in fact, weaker than 0.8. The smallest effect size with which we will have 80% power to detect is a 6.5% reduction in the rate of unprotected sex. Technically speaking, our study will have greater power than what is reported here after we adjust for our blocked design. In conclusion, we will have 80% power to detect an effect size equal to half of what we observed in our pilot trial and less than half of the lower bound of effect sizes seen in other HIV prevention programs with MSM²⁶. For our primary biomedical endpoint of STI incidence, we assume the annual incidence based on our longitudinal cohort studies in the range of 10 to 15%. If the incidence rate in the control group is 10%, we will have 81%, 70%, and 56% power to detect an incidence reduction of 7%, 6%, and 5%, respectively. If the incidence rate in the control group is higher, say 15%, then the power reduces to 71%, 60%, and 47%, respectively. The objective of aim 3 is to estimate the intervention effect among subgroups and test for significant differences. In data analyses, this will be achieved by testing 2-way interactions, treatment by subgroup. For a conservative power calculation, we repeated the power calculations as per aim 1 with a reduced sample size. Assuming N=200 per group (say, for racial/ethnic subgroups), an ERR=0.89 as above, and strong correlation among repeated measures (i.e. 0.8), we will have 91%, 85%, and 77% power to detect a 10%, 9%, and 8% reduction in the rate of unprotected sex among YMSM, respectively, due to KIU! intervention. The power will be less for effect sizes more subtle than 8% and less for smaller subgroups. In addition to racial/ethnic subgroups, other subgroups of interest include sexual orientation identity groups (81%

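### The stated powers for the behavioural primary cannot come from one standard error, and on the time-averaged formula the 97% needs near-Poisson variance that does not fit a Poisson random-intercept model at correlation 0.8

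*Protocol*

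**What the plan says.** Protocol B.12 describes its calculations as "using common sample size formula for repeated measures" and "with nominal Type I error rates" (0.05, sidedness not given). It plans to "enroll 900 YMSM, and assume 80% retention based on our preliminary studies". The main claim is "we will have 97% power to detect a 11% reduction in the rate of unprotected sex (ERR = 0.89) due to the intervention", with a correlation of 0.8 between repeated measures, followed by the reassurance that "our power calculation is conservative if the correlation among repeated measures is, in fact, weaker than 0.8". The same paragraph gives 80% power at a 6.5% reduction and, for subgroups with N=200 per group, 91%, 85% and 77% power at reductions of 10%, 9% and 8%.

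SAP A.5 repeats these figures but adds an allocation, "KIU! condition n=375; control arm n=375". The protocol's Study Design section has "KIU! condition n=450; control arm n=450".

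The planned analysis (Protocol B.11, SAP C3) is a mixed model suited to the outcome's distribution, with normal and Poisson named. It has a random intercept and a group effect averaged over time. On baseline it says: "The baseline value of the outcome and other required covariates at baseline will be included as additional independent variables". Neither document states a planning mean, standard deviation or dispersion for the power calculation. Table 1 of the protocol gives pilot means at 3 months of 3.70 (KIU!) and 6.20 (control), without SDs.

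**The concern.** Power at two effect sizes for one outcome, one design and one sample size must follow from a single standard error. Here it does not appear to. The 97% also looks high for a count outcome that varies strongly between men, which is what a correlation of 0.8 implies. The correlation remark is given without conditions, although its direction depends on the formula and on how the variance behaves.

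This paragraph is the only justification of power for the behavioural primary, and it stands in both documents. If its figures cannot be traced to stated inputs, a null result cannot be read against them. Nobody could say which reduction the trial was able to exclude.

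**Working it through.** **Inputs.** From B.12: two-sided α 0.05 (sidedness assumed), 900 enrolled, 80% retained, so 720 or 360 per arm; ρ = 0.8; reductions of 11% and 6.5%. From B.11: three follow-ups. Assumed: control mean 6.2, the pilot 3-month value. Power = Φ(d/SE − 1.96).

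**1. Reproducing the 97%.** Time-averaged comparison without baseline, variance factor (1+2ρ)/3 = 0.867, Poisson variance 6.2:
- d = 0.11 × 6.2 = 0.682; SE = √(2 × 6.2 × 0.867/360) = 0.173; power 97.7% (98.2% on the log scale).
- Exactly 97% needs an SD of about 2.56, that is a variance/mean ratio of about 1.1.
- On this same reading a 6.5% reduction (d = 0.403) has 65–66% power, not 80%. The N=200 figures become 78%, 69% and 59% (log scale), not 91%, 85% and 77%.

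**2. Consistency, needing no mean or dispersion.**
- 97% at 11%: −ln 0.89 = 0.1165; SE = 0.1165/(1.960 + 1.881) = 0.0303. At 6.5%, −ln 0.935 = 0.0672, so power is 60%. On the linear scale, 0.065 × 3.841/0.11 − 1.96 = 0.31, or 62%. Power of 80% is reached at 0.11 × 2.802/3.841 = 8.0%.
- 80% at 6.5%: SE = 0.0672/2.802 = 0.0240. At 11%, 0.1165/0.0240 − 1.96 = 2.9, or 99.8%.
- One-sided α does not help: 0.0672 × (1.645 + 1.881)/0.1165 − 1.645 = 0.39, or 65% at 6.5%.

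**3. Subgroup figures (N=200 per group).**

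| Reduction | Stated power | Implied SE (log) | n per group giving SE 0.0303 | n per group giving SE 0.0240 |
|---|---|---|---|---|
| 10% | 91% | 0.0319 | 221 | 354 |
| 9% | 85% | 0.0315 | 215 | 344 |
| 8% | 77% | 0.0309 | 207 | 332 |

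Read as 200 per arm, these fit the 6.5% claim at 332–354 per arm, near the 360 retained. They fit the 97% claim only at 207–221.

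**4. Arm size.** 80% of 450 is 360; 80% of 375 is 300. If 97% is right at 360, the SE at 300 is 0.0303 × √(360/300) = 0.0332, and power is Φ(0.1165/0.0332 − 1.96) = 94%. The SAP's 375 + 375 = 750 also disagrees with its own 900 enrolled.

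**5. Variance under a Poisson random intercept.** Within-man variance is at least the mean, so ρ = 0.8 requires total variance of at least 6.2/(1 − 0.8) = 31, a ratio of 5. At 31, with baseline-adjusted factor (1+2ρ)/3 − ρ² = 0.227:

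| Retained per arm | No baseline (0.867) | Baseline-adjusted (0.227) |
|---|---|---|
| 360 | 42% | 93% |
| 300 | 36% | 88% |

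Log-scale versions at 360 give 44% and 94%; a simulation of gamma-Poisson counts gave 45% and 95%.

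**6. Direction of the correlation effect** (baseline-adjusted, 360 per arm):

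| ρ | Variance fixed at 31 | Variance 6.2/(1 − ρ) |
|---|---|---|
| 0.8 | 93% | 93% |
| 0.65 | 80% | 96% |
| 0.5 | 72% | 98% |
| 0.33 | 69% | 99.5% |

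In the time-averaged formula without baseline, weaker correlation always raises power at a given variance: 97.7% at 0.8 and 99.4% at 0.5 with Poisson variance.

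**The case against.** The 97%, the correlation of 0.8 and the conservative remark do agree arithmetically on one ordinary reading: Poisson variance, mean 6.2, averaged follow-ups and no baseline term. Marginal sample-size formulas take variance and correlation as separate inputs, and Poisson marginals with correlation 0.8 are mathematically possible. The cited formula is not reproduced in the documents, and the planning mean is ours; at 3.7, Poisson variance gives 88%. All of this stands. A reader might infer that the three statements can never hold together, but step 1 shows that they can.

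A reader might also infer that the correlation remark is simply backwards under the planned baseline-adjusted model. That is so only if total variance stays fixed while the correlation falls. If the variance is tied to the correlation, as the argument in step 5 implies, the remark has the right direction. The documents do not say which applies.

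None of this touches step 2, which uses neither mean nor dispersion. The 6.5% and subgroup figures might have been run with other inputs, but B.12 reports no second set. If N=200 means the whole subgroup (100 per arm), the matching sizes in step 3 halve, and the fit to the 6.5% claim is lost as well.

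**Conclusion.** The concern holds in two parts. The first is firm: 97% at 11% and 80% at 6.5% cannot share a standard error (0.0303 against 0.0240), and the N=200 subgroup figures imply about 0.031, nearly the full-trial value. At least one stated figure is wrong or rests on unreported inputs. The documents do not show which; read as 200 per arm, the subgroup figures sit closer to the 6.5% claim.

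The second part is conditional on a planning mean of 6.2 and a Poisson random-intercept model. The variance behind the time-averaged 97% (ratio about 1.1) does not fit that model at correlation 0.8 (ratio at least 5). At that minimum ratio, power for an 11% reduction is about 42% without baseline adjustment and 93% with it (36% and 88% at 300 per arm).

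It would go too far to conclude that the trial is underpowered. With the planned baseline adjustment and this minimum variance, power at 11% remains around 90%, and the actual dispersion is unknown. The correlation remark is true under some conditions and false under others, so it cannot stand unqualified.

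**What to change.** In Protocol B.12 and SAP A.5, state one formula, the control mean, the dispersion, the sidedness of α and the retained number per arm, with 450 or 375 settled. From these inputs recompute the 97%, 6.5% and subgroup figures for the planned baseline-adjusted overdispersed-count model over correlations from 0.3 to 0.8, and replace the inconsistent figures in both documents. Say whether N=200 is per arm or per subgroup. State the condition under which weaker correlation is conservative, or remove the remark.

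The cost is one recalculation and text in two documents, with no additional participants. The downside is that some stated figures may become less favourable.
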